7.4.1.3 Dose Delay Criteria for Sunitinib

Sunitinib dose delays should be based on instructions in the approved product label and should be considered for any severe or intolerable drug-related adverse events.

Within a cycle, missed doses of sunitinib should be skipped. Participants should never be dosed during the 2-week off period of each 6-week cycle, even if treatment delays occurred earlier in the cycle and therapy is ready to be resumed. If treatment is delayed past the end of the 6-week cycle, the start of the next cycle should be delayed until treatment with sunitinib resumes.

Prior to resuming therapy after a dose delay, refer to [Section 7.4.2](#) for dose reduction recommendations and [Section 8](#) for discontinuation criteria.

For this protocol, sunitinib dosing should be delayed for any of the following:

- Urine protein/creatinine ratio (UPCR) ≥ 2.0 or urine dipstick protein $\geq 3+$ or urine protein ≥ 2.0 g / 24 hours. Obtain 24 hour urine protein prior to next dosing visit.
- Grade 3 prolonged QTc interval (ie, QTcF interval > 500 msec on at least 2 out of 3 separate ECGs performed at least 3 minutes apart)
- Any Grade 2 or 3 drug-related venous thrombosis requiring anticoagulation, with the following exception:
 - Any recurrent or worsening venous thromboembolic event after restarting sunitinib will require discontinuation
- Any other Grade 2 drug-related adverse event that persists or worsens despite supportive care management, with the following exception:
 - Any Grade 2 drug-related hemorrhage requires dose delay
 - Grade ≥ 2 arterial thromboembolic events, including cerebrovascular ischemia, cardiac ischemia/infarction, peripheral or visceral arterial ischemia, require discontinuation
- Grade 3 drug-related hypertension (systolic BP ≥ 160 mm Hg or diastolic BP ≥ 100 mm Hg). NOTE: Stopping or reducing the dose of sunitinib is expected to cause a decrease in BP. The

treating physician should monitor the participant for hypotension and adjust the number and dose of antihypertensive medications accordingly.

- Any other Grade 3 drug-related adverse event or laboratory abnormality, with the following exceptions:
 - Grade \geq 3 drug-related hemorrhage requires discontinuation (Section 8.1.2).
 - Drug-related AST or ALT $>$ 8 x ULN requires discontinuation (Section 8.1.2).
 - Concurrent AST or ALT $>$ 3 x ULN and total bilirubin $>$ 2 x ULN, consistent with potential drug-induced liver injury (see Section 9.2.7), requires discontinuation (Section 8.1.2)
 - Grade 3 drug-related amylase or lipase abnormalities that are not associated with symptoms or clinical manifestations of pancreatitis do not require dose delay. In such cases, more frequent monitoring (eg, weekly) of amylase and lipase is recommended. If amylase or lipase worsen to Grade 4 severity or the participant develops symptoms or clinical manifestations of pancreatitis, dosing should be delayed.
- Grade 4 drug-related amylase or lipase abnormalities require dose delay. Participants should be monitored for development of symptoms or clinical manifestations of pancreatitis.
- Grade 4 drug-related electrolyte abnormalities require dose delay. Electrolyte correction with supplementation/appropriate management should be promptly initiated.
- Grade 4 drug-related neutropenia, lymphopenia, leukopenia, anemia, or thrombocytopenia
- Any adverse event, laboratory abnormality, or intercurrent illness which, in the judgment of the investigator, warrants delaying sunitinib dosing
- For participants scheduled for major surgery, including dental surgery which may impact bone healing, sunitinib dosing should be delayed at least 28 days prior to scheduled surgery. The treating physician should use clinical judgment with regard to the risks and benefits of the planned surgical procedure if it is not possible to delay sunitinib dosing for 28 days prior to the procedure. A delay of sunitinib dosing of 5 to 7 days is recommended for healing for minor surgery.

As a general approach, all AEs related to sunitinib should be managed with supportive care when possible at the earliest signs of toxicity. Calcium, magnesium, potassium, and phosphorus should be kept above the lower limits of the laboratory normal values. Please refer to the sunitinib approved product label and Appendix 10 for additional information regarding AE monitoring and management.

7.4.2 Dose Reductions and Escalations

Dose reductions are permitted for cabozantinib and sunitinib but not for nivolumab and ipilimumab (see Table 7.4.2-1).

Table 7.4.2-1: Dose Level Modifications Table

Dose Level	Cabozantinib (tablet dose expression)	Sunitinib (capsule dose expression)	Nivolumab (IV)	Ipilimumab (IV)	Nivolumab (IV)
0 (starting dose)	40 mg daily	50 mg daily	3mg/kg	1 mg/kg	240 mg

Table 7.4.2-1: Dose Level Modifications Table

Dose Level	Cabozantinib (tablet dose expression)	Sunitinib (capsule dose expression)	Nivolumab (IV)	Ipilimumab (IV)	Nivolumab (IV)
-1	20 mg daily	37.5 mg daily	-	-	-
-2	20 mg every other day	25 mg daily	-	-	-

7.4.2.1 Dose Reduction and Escalation for Nivolumab and Ipilimumab

No dose reductions or dose escalations of nivolumab or ipilimumab are allowed.

7.4.2.2 Dose Reduction and Escalation for Cabozantinib

Dose reductions and dose escalations for adverse event management are allowed for cabozantinib (Table 7.4.2-1). Cabozantinib doses will not be re-escalated once reduced, unless a concomitant strong CYP3A4 inducer is started (see below). The only exception is participants who continue on cabozantinib alone after discontinuation of nivolumab alone (Arm A) or discontinuation of both nivolumab and ipilimumab (Arm B) who may re-escalate one dose level if the prior dose reduction was due to a toxicity felt by the investigator to have been mainly related to nivolumab and/or ipilimumab.

After toxicity requiring a dose delay has improved and meets the criteria to resume dosing (Section 7.4.3.2), participants who were receiving cabozantinib 40 mg daily prior to the delay will resume cabozantinib at 20 mg daily. Participants who were receiving cabozantinib 20 mg daily prior to the delay and require another dose delay will resume cabozantinib at 20 mg every other day. If more than 2 dose reductions are necessary (ie, reduction to less than 20 mg every other day), cabozantinib must be permanently discontinued (Section 8.1.2).

Participants who required a dose delay due to Grade 3 hypertension, which improved with antihypertensive medications, or any Grade 2 or 3 drug-related adverse event or asymptomatic laboratory abnormality that improved to Grade ≤ 1 within 7 days with supportive medical care may resume cabozantinib at the same dose or a reduced dose, at the discretion of the investigator.

Participants with asymptomatic Grade 2 drug-related AST, ALT or total bilirubin elevation, or Grade 3 drug-related lipase or amylase abnormalities that are not associated with symptoms or clinical manifestations of pancreatitis may reduce cabozantinib by one dose level, without delaying dosing, at the discretion of the investigator. See also section 7.4.1.2.

In Participants Who Start Taking a Concomitant Strong CYP3A4 Inhibitor: Reduce the daily cabozantinib dose by 20 mg (for example, from 40 mg to 20 mg daily). Resume the dose that was used prior to initiating the CYP3A4 inhibitor 2 to 3 days after discontinuation of the strong inhibitor (see Prescribing Information for cabozantinib).

7.4.2.3 Dose Reduction and Escalation for Sunitinib

Sunitinib Dose Reductions are permitted as per the approved product label for safety reasons or when a concomitant strong CYP3A4 inhibitor is needed (Appendix 9). Selection of an alternative

concomitant medication with minimal or no enzyme inhibition potential is recommended whenever possible.

After toxicity requiring a dose delay has improved and meets the criteria to resume dosing (Section 7.4.3.3), participants should resume sunitinib at one dose level reduction. Dose reductions should occur in 12.5 mg decrements. No more than 2 dose reductions are allowed. If more than 2 dose reductions are necessary (ie, reduction to less than 25 mg daily), the participant must be permanently discontinued (Section 8.1.3).

Participants who required a dose delay due to Grade 3 hypertension, which improved with antihypertensive medications, or any Grade 2 or 3 drug-related adverse event or asymptomatic laboratory abnormality that improved to Grade ≤ 1 within 7 days with supportive medical care may resume sunitinib at the same dose or a reduced dose, at the discretion of the investigator.

At the time a dose reduction is considered, also refer to Section 7.4.2.3 for dose delay recommendations and Section 8.1.3 for discontinuation criteria.

Sunitinib Dose Escalations are permitted as per the approved product label when a concomitant CYP3A4 inducer is needed (Appendix 9). Selection of an alternative concomitant medication with minimal or no enzyme induction potential is recommended whenever possible.

7.4.3 Criteria to Resume Treatment

7.4.3.1 Criteria to Resume Nivolumab and Ipilimumab Treatment

Delayed doses of nivolumab and/or ipilimumab should be administered as soon as the participant meets criteria to resume treatment. If a dose has been delayed, the participant should not wait until the next scheduled dosing date.

Participants may resume treatment with study drug when the drug-related AE(s) resolve to Grade ≤ 1 or baseline value, with the following exceptions:

- Participants may resume treatment in the presence of Grade 2 fatigue.
- Participants who have not experienced a Grade 3 drug-related skin AE may resume treatment in the presence of Grade 2 skin toxicity.
- For participants with Grade 2 AST, ALT, and/or total bilirubin abnormalities, dosing may resume when laboratory values return to baseline and management with corticosteroids, if needed, has been completed.
- Drug-related pulmonary toxicity, diarrhea, or colitis, must have resolved to baseline before treatment is resumed. Participants with persistent Grade 1 pneumonitis after completion of a steroid taper over at least 1 month may be eligible for retreatment if discussed with and approved by the BMS Medical Monitor or designee.
- Drug-related endocrinopathies adequately controlled with only physiologic hormone replacement may resume treatment.
- If treatment is delayed > 6 weeks, the participant must be permanently discontinued from study therapy, except as specified in Section 8.1.1.

For Arm B participants who delay nivolumab and ipilimumab dosing after Cycle 1 or 2, both nivolumab and ipilimumab must be resumed on the same day when the criteria to resume treatment are met.

For Arm B participants who delay nivolumab and ipilimumab dosing after Cycle 3 due to any drug-related AE meeting dose delay criteria that does not resolve within 14 days or requires treatment with systemic corticosteroids, it is acceptable to omit Cycle 4 if the investigator feels that ipilimumab was the main cause of the toxicity requiring dose delay. In this situation, when the participant meets criteria to resume nivolumab, the participant may proceed to Cycle 5 and begin nivolumab monotherapy maintenance.

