7.4.1.1 Dose Delay Criteria for Nivolumab and Ipilimumab

In Arm A, nivolumab administration should be delayed, and in Arm B, both nivolumab and ipilimumab administration should be delayed, for any of the following:

- Any Grade ≥ 2 non-skin, drug-related AE, with the exception of fatigue
- Grade 2 drug-related creatinine, AST, ALT, and/or total bilirubin abnormalities
- Any Grade 3 skin, drug-related AE
- Any Grade 3 drug-related laboratory abnormality, with the following exceptions:
 - Grade 3 lymphopenia does not require dose delay
 - Grade 3 amylase or lipase abnormalities that are not associated with symptoms or clinical manifestations of pancreatitis do not require a dose delay.
 - Grade ≥ 3 AST, ALT or total bilirubin will require dose discontinuation (see section 8.1.1)
- Any adverse event, laboratory abnormality, or intercurrent illness which, in the judgment of the investigator, warrants delaying the dose of study medication.

During Cycles 1-4 in Arm B, both nivolumab and ipilimumab must be delayed at the same time.

Immuno-oncology agents, such as nivolumab and ipilimumab, are associated with AEs that differ in severity and duration than AEs caused by other therapeutic classes. Early recognition and management of AEs associated with immuno-oncology agents may mitigate severe toxicity. Management Algorithms have been developed to assist investigators in assessing and managing the following groups of AEs:

- Gastrointestinal
- Renal
- Pulmonary

- Hepatic
- Endocrinopathy
- Skin
- Neurological

The management algorithms recommended for use in CA2099ER are included in [Appendix 5](#).

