7.4.1.2 Dose Delay Criteria for Cabozantinib

Cabozantinib dosing should be delayed for the following:

- Urine protein/creatinine ratio (UPCR) > 2.0 *or* urine dipstick protein \geq 3+ *or* urine protein > 2.0 g / 24 hours. Obtain 24 hour urine protein prior to next dosing visit.
- Grade 3 prolonged QTc interval (ie, QTcF interval > 500 msec on at least 2 out of 3 separate ECGs performed at least 3 minutes apart)
- Any Grade 2 or 3 drug-related venous thrombosis requiring anticoagulation, with the following exception:
 - Any recurrent or worsening venous thromboembolic event after restarting cabozantinib will require discontinuation
- Any other Grade 2 drug-related adverse event or grade 2 drug-related laboratory abnormality (e.g., AST, ALT, total bilirubin) that persists for more than 1 week or worsens despite supportive care management, with the following exception:
 - Any Grade 2 drug-related hemorrhage requires dose delay
 - Grade \geq 2 arterial thromboembolic events, including cerebrovascular ischemia, cardiac ischemia/infarction, peripheral or visceral arterial ischemia, require discontinuation
- Sustained Grade 3 drug-related hypertension (systolic BP \geq 160 mm Hg or diastolic BP \geq 100 mm Hg). NOTE: Stopping or reducing the dose of cabozantinib is expected to cause a decrease in BP. The treating physician should monitor the participant for hypotension and adjust the number and dose of antihypertensive medications accordingly.
- Any other Grade 3 drug-related adverse event or laboratory abnormality, with the following exceptions:
 - Grade \geq 3 drug-related hemorrhage requires discontinuation ([Section 8.1.2](#)).
 - Drug-related AST or ALT > 8 x ULN requires discontinuation ([Section 8.1.2](#)).
 - Concurrent AST or ALT > 3 x ULN and total bilirubin > 2 x ULN, consistent with potential drug-induced liver injury (see [Section 9.2.7](#)), requires discontinuation ([Section 8.1.2](#))
 - Grade 3 drug-related amylase or lipase abnormalities that are not associated with symptoms or clinical manifestations of pancreatitis do not require dose delay. In such cases, more frequent monitoring (eg, weekly) of amylase and lipase is recommended. If amylase or lipase worsen to Grade 4 severity or the participant develops symptoms or clinical manifestations of pancreatitis, dosing should be delayed.

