8.1.1 Nivolumab and Ipilimumab Dose Discontinuation (Arms A and B)

CA2099ER Global Revised Protocol 01

Implementation of CA2099ER Global Revised Protocol 01 stops further randomization into Arm B. Participants previously randomized to Arm B continue with Arm B treatment and continue with Arm B clinical planned events, per protocol.

The assessment for discontinuation of nivolumab, ipilimumab, and cabozantinib should be made separately for each study drug. Although there is overlap among the discontinuation criteria, if

discontinuation criteria are met for one study drug but not the other(s), it may be acceptable to continue treatment with the study drug(s) that are not felt to be related the toxicity, as specified below. If the investigator considers the toxicity to be related to all study drugs or is unable to determine which of the study drug(s) in Arm A or Arm B are the cause of toxicity, then all study drugs in the treatment regimen should be discontinued, and the recommendations for management of toxicity related to all study drugs should be promptly initiated.

Nivolumab and/or ipilimumab treatment should be permanently discontinued for any of the following:

- Any Grade 2 drug-related uveitis, eye pain or blurred vision that does not respond to topical therapy and does not improve to Grade 1 severity within the re-treatment period OR requires systemic treatment
- Any Grade 3 non-skin, drug-related adverse event lasting > 7 days, or recurs with the following exceptions for laboratory abnormalities, diarrhea, colitis, neurologic toxicity, drug-related uveitis, pneumonitis, bronchospasm, hypersensitivity reactions, infusion reactions, and endocrinopathies:
 - Grade 3 drug-related diarrhea, colitis, neurologic toxicity, uveitis, pneumonitis, bronchospasm, myocarditis, hypersensitivity reaction, or infusion reaction of any duration requires discontinuation. NOTE: The diagnosis of colitis should be supported by findings on colonoscopy whenever possible.
 - Grade 3 drug-related endocrinopathies, adequately controlled with only physiologic hormone replacement do not require discontinuation. Adrenal insufficiency requires discontinuation regardless of control with hormone replacement.
 - Grade 3 drug-related laboratory abnormalities do not require treatment discontinuation except:
 - ◆ Grade 3 drug-related thrombocytopenia > 7 days or associated with bleeding requires discontinuation

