 - ◆ Any drug-related liver function test (LFT) abnormality that meets the following criteria require discontinuation:
 - Grade ≥ 3 drug-related AST, ALT or Total Bilirubin requires discontinuation*
 - Concurrent AST or ALT > 3 x ULN and total bilirubin > 2x ULN
- Any Grade 4 drug-related adverse event or laboratory abnormality (including but not limited to creatinine, AST, ALT, or Total Bilirubin), except for the following events which do not require discontinuation:
 - Grade 4 neutropenia ≤ 7 days
 - Grade 4 lymphopenia or leukopenia or asymptomatic amylase or lipase

- Isolated Grade 4 electrolyte imbalances/abnormalities that are not associated with clinical sequelae and are corrected with supplementation/appropriate management within 72 hours of their onset
- Grade 4 drug-related endocrinopathy adverse events, such as, hyper- or hypothyroidism, or glucose intolerance, which resolve or are adequately controlled with physiologic hormone replacement (corticosteroids, thyroid hormones) or glucose-controlling agents, respectively, may not require discontinuation after discussion with and approval from the BMS Medical Monitor or designee.
- Any event that leads to delay in dosing lasting > 6 weeks from the previous dose requires discontinuation, with the following exceptions:
 - Dosing delays to allow for prolonged steroid tapers to manage drug-related adverse events are allowed.
 - Dosing delays lasting > 6 weeks from the previous dose that occur for non-drug-related reasons may be allowed if approved by the BMS Medical Monitor or designee.

Prior to re-initiating treatment in a participant with a dosing delay lasting > 6 weeks, the BMS Medical Monitor or designee must be consulted. Tumor assessments should continue as per protocol even if dosing is delayed. Periodic study visits to assess safety and laboratory studies should also continue every 6 weeks or more frequently if clinically indicated during such dosing delays.

- Any adverse event, laboratory abnormality, or intercurrent illness which, in the judgment of the Investigator, presents a substantial clinical risk to the participant with continued nivolumab dosing.

Participants in Arm B who meet any of the discontinuation criteria above prior to Cycle 3 must discontinue both nivolumab and ipilimumab and may not receive nivolumab monotherapy maintenance.

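### For nivolumab, a concurrent AST/ALT and bilirubin rise below Grade 3 but above the 8.1.1 limits falls under both permanent discontinuation (8.1.1) and delay-then-resume (7.4.1.1, 7.4.3.1)

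*Protocol*

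**What the plan says.** **Discontinuation (Protocol 8.1.1).** The list opens: "Nivolumab and/or ipilimumab treatment should be permanently discontinued for any of the following". Its liver item begins "Any drug-related liver function test (LFT) abnormality that meets the following criteria require discontinuation" and has two bullets. The first is Grade 3 or higher "drug-related AST, ALT or Total Bilirubin requires discontinuation". The second carries no grade: "Concurrent AST or ALT > 3 x ULN and total bilirubin > 2x ULN".

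**Delay (Protocol 7.4.1.1).** Nivolumab, and in Arm B also ipilimumab, is delayed for "Grade 2 drug-related creatinine, AST, ALT, and/or total bilirubin abnormalities". The section refers liver values to 8.1.1 only when they are Grade 3 or higher.

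**Resumption (Protocol 7.4.3.1).** "For participants with Grade 2 AST, ALT, and/or total bilirubin abnormalities, dosing may resume when laboratory values return to baseline", provided any corticosteroid management is finished. The same section asks for a delayed dose to be given as soon as the resume criteria are met. Its one reference to 8.1.1 concerns delays longer than 6 weeks.

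**Other drugs.** The cabozantinib delay section (7.4.1.2) names the combined finding, "Concurrent AST or ALT > 3 x ULN and total bilirubin > 2 x ULN, consistent with potential drug-induced liver injury", as requiring discontinuation. The sunitinib delay section (7.4.1.3) does the same. Neither drug's resume section (7.4.3.2, 7.4.3.3) mentions it.

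**The concern.** A site handling a liver abnormality on nivolumab would normally go from the delay criteria to the resume criteria. On that route nothing warns that a combined AST/ALT and bilirubin rise may already have met a permanent stopping rule. A site that starts from 8.1.1 reaches the opposite outcome for the same laboratory values.

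The stake is mainly participant safety. The 8.1.1 limits are the enzyme and bilirubin limits in the protocol's definition of potential drug-induced liver injury (9.2.7), and cabozantinib, the other drug in Arm A, has liver stopping rules of its own. There is a smaller reporting consequence. Adverse events leading to discontinuation are a safety endpoint, and SAP 7.6.3 splits them in Arm A into cabozantinib only, nivolumab only and both, so inconsistent handling would reach those tables.

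**Working it through.** The plan gives no figure to reproduce here, so the check sets the rules side by side.

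**Step 1. When does the concurrent bullet matter?** Any AST, ALT or bilirubin value of Grade 3 or higher already stops nivolumab under the first liver bullet of 8.1.1. The concurrent bullet therefore adds something only when every liver value is below Grade 3.

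**Step 2. What do the 7.4 sections do below Grade 3?** They send Grade 2 abnormalities to delay and then possible resumption, and they name the combined case through the and/or wording. No exception is made for values above the 8.1.1 limits.

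**Step 3. Where do the rules part?** For drug-related values:

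| Finding | 7.4.1.1 and 7.4.3.1 | 8.1.1 | Consistent? |
|---|---|---|---|
| Any of the three at Grade 3 or higher | Referred to 8.1.1 | Stop | Yes |
| One Grade 2, the other normal | Delay, may resume | Criterion not met | Yes |
| Both Grade 2, bilirubin not above 2 x ULN | Delay, may resume | Criterion not met | Yes |
| Both Grade 2, AST or ALT > 3 x ULN and bilirubin > 2 x ULN | Delay, may resume | Stop | **No** |

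**Step 4. Size of the band.** The documents do not state the grade limits. Assume Grade 2 means above 3 and up to 5 x ULN for AST/ALT, and above 1.5 and up to 3 x ULN for bilirubin. Intersecting these with 8.1.1:

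- AST/ALT: lower limit max(3, 3) = 3, upper limit 5, so above 3 and up to 5 x ULN.
- Bilirubin: lower limit max(1.5, 2) = 2, upper limit 3, so above 2 and up to 3 x ULN.

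An ALT of 4 x ULN with bilirubin of 2.5 x ULN lies inside the band. The lower limits come from 8.1.1 and only the upper limits are assumed. The band is not empty as long as Grade 3 starts above 3 x ULN for AST/ALT and above 2 x ULN for bilirubin.

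**Step 5. Does another passage settle it?** Section 7.4.1 tells sites to resume when the 7.4.3 criteria are met. Section 7.4 refers in general terms to Section 8 for nivolumab modifications. Section 8.1 makes the 8.1.1 criteria mandatory. None of these addresses the combined Grade 2 case. For sunitinib, by contrast, 7.4.1.3 tells the reader to consult the Section 8 discontinuation criteria before resuming.

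**The case against.** The best counter-argument is that the protocol already orders these rules. Section 8.1 is mandatory for anyone meeting an 8.1.1 criterion, 7.4.3.1 is only permissive, and 7.4 says nivolumab is modified under Section 8 as well. Section 7.4.3.1 also leaves out other 8.1.1 stops: it allows resumption after diarrhea, colitis or pulmonary toxicity has returned to baseline, while 8.1.1 stops Grade 3 diarrhea, colitis or pneumonitis of any duration. On that view 7.4.3.1 applies only to participants who have not met 8.1.1.

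This is a plausible reading, and it lowers the severity. It does not remove the problem. The diarrhea, colitis and pulmonary bullet names no grade, so it can be confined to the cases that 8.1.1 leaves open. The liver bullet names Grade 2 and the combined case expressly, and the section then directs prompt re-dosing.

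A second argument is that the concurrent bullet sits beneath the Grade 3 laboratory exceptions in 8.1.1 and so applies only there. Its lead-in refers to any drug-related liver test abnormality, and confining it to Grade 3 would make it redundant.

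Third, 7.4.1.1 points to management algorithms in Appendix 5, including a hepatic one. That appendix is not in the supplied text and may address combined elevations, so this limitation stands.

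There are also safeguards. Potential drug-induced liver injury is reported as an SAE, SAEs go to the sponsor within 24 hours, and Section 9 requires immediate safety concerns to be discussed with the sponsor to decide whether treatment continues.

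**Conclusion.** The overlap is present in the current text and confined to one band: concurrent elevations below Grade 3 but above the 8.1.1 limits, about 3 to 5 x ULN for AST/ALT with about 2 to 3 x ULN for bilirubin on the assumed grade limits. Frequency is not given. This is a should-fix clarification.

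A reader might infer more, and the documents do not support it:

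- **That everyone with both values raised below Grade 3 is affected.** Grade 1 elevations, and bilirubin of 1.5 to 2 x ULN, do not meet the 8.1.1 criterion.
- **That every case is potential drug-induced liver injury.** The limits match 9.2.7, but that definition also requires no initial cholestasis and no other apparent cause. The nivolumab bullet in 8.1.1 does not use the term.
- **That sites will act differently.** The text permits this. Section 8.1 and the sponsor-contact requirements may prevent it.
- **That the cabozantinib text is a complete model.** It names the criterion only in the delay section, as an exception under Grade 3 events. Its Grade 2 bullet and its resume section do not carry it.

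No view is taken on which clinical rule is right.

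**What to change.** Reconcile 7.4.1.1, 7.4.3.1 and 8.1.1 so that a drug-related concurrent AST/ALT and bilirubin elevation below Grade 3 has one stated outcome, chosen by the sponsor. Add a cross-reference to 8.1.1 for this case in both nivolumab 7.4 sections, and check that the hepatic algorithm in Appendix 5 agrees. The cabozantinib and sunitinib delay sections show that the criterion can be named there, but they offer no wording for the resume section.

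The cost is a few words in two bullets at the next amendment and a clarification letter to sites. Sample size, alpha, event targets and planned analyses are unaffected.
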